4.3 Trial Periods

The total duration of the study is expected to 16 weeks [REDACTED]

4.4 Visit Windows

Study visits are expected to occur according to the protocol schedule. All data will be tabulated per the evaluation visit as recorded on the eCRF even if the assessment is outside of the visit window. In data listings, the relative study day of all dates will be presented.

4.5 Handling of Missing Data

Study data will be presented based on observed cases, i.e. no imputation of missing values will be performed.

4.6 Site Pooling

There will be no pooling of centers.

4.7 Multiple Comparisons/Multiplicity

No adjustments for multiple comparisons or multiplicity will be made. P-values obtained for any endpoint other than the primary will only be provided for ease of interpretation of the results.

	
Title 05DF2004 SAP Advanced Clinical
	
Doc id [REDACTED]

--	--	------------------------------

Sponsor: Galderma

Protocol Number: CTN 05DF2004

Plan Version: 1.0

4.8 Interim Analysis and Data Monitoring

No interim analysis is planned for this study.

5.0 ANALYSIS POPULATIONS

The Analysis Populations to be used for the analyses in this study are described below.

5.1 Full Analysis Set (FAS)

Includes all subjects who were injected in both cheeks. FAS is the primary population for all effectiveness analyses.

5.2 Per-Protocol Population

If there are any clinical study protocol (CSP) deviations considered to have substantial impact on the effectiveness outcome, a per protocol (PP) population excluding those subjects may be defined.

5.3 Safety Population

The Safety Population includes subjects who were injected in at least one cheek. Safety analysis is performed based on the safety population set.

6.0 SUBJECT STATUS

6.1 Subject Disposition

Subject disposition will be summarized by treatment group and overall. The number of subjects screened, randomized, and treated will be presented as well as the number of subjects in each analysis population (FAS, Safety, and PP). The number and percentage of subjects in the FAS population who complete the study will be summarized, along with the number and percentage of subjects who did not complete the study for each discontinuation reason as specified on the eCRFs.

All withdrawn subjects will be listed including subject number, date, reason for withdrawal, and last visit performed.

Inclusion/exclusion data also will be presented by subject in a data listing.

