5.5 Withdrawal of subjects

An Investigator may decide to discontinue a subject from the clinical study for safety reasons.

Although the importance of completing the entire clinical study should be explained to the subject by the clinical study personnel, any subject is free to discontinue participation in this clinical study at any time and for whatever reason, specified or unspecified, and without any prejudice. No constraints are to be imposed on the subject, and when appropriate, a subject may be treated with other conventional therapy when clinically indicated.

When a subject does not complete the clinical study, he/she will be fully assessed, if such assessment is possible. The procedures designated for the Early Termination (ET) visit should be completed for all subjects discontinuing the clinical study and the appropriate eCRF should be completed.

All discontinuations and the reason for discontinuation are to be documented by the Investigator.

For discontinuation due to an AE, the Adverse Event form is to be completed. The Investigator should also ensure that the subject receives suitable therapy for the AE.

Pregnancies occurring during the screening period are considered as screening failures; they should be recorded as such in the eCRF and no pregnancy form is to be completed.

In case of a pregnancy occurring after the baseline visit, the procedures described in Section 8.2.8 should be followed. The subject may remain in the study, but no invasive procedure should be conducted.

The Sponsor may also decide to prematurely terminate or suspend a subject's participation in the clinical study.

6. Study Product

The term "study product" refers to Restylane Volyme and Restylane Lyft Lidocaine.

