10.8 Withdrawals and deviations

All withdrawn subjects will be listed individually, including at least subject number, date and reason for withdrawal, and last visit performed.

Subjects with CSP deviations will be listed individually, including subject number and observed deviation. Depending on the seriousness of the deviation, subject might be excluded from the PP population, which shall be documented prior to database lock.

Deviations from the statistical plan will be documented in the statistical report.

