7.3 Drug Exposure and Compliance

Data for injection characteristics will be summarized for initial treatment and optional touch-up for the safety population. The following parameters will be summarized for extent of exposure:

- Injection Volume and Total Injection Volume (initial plus touch up)
- Injection Depth
- Injection Method
- Needle Size

The extent of exposure data will also be presented by subject in a data listing.

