By-subject listings also will be provided for all subjects (safety population) for the following: AEs related to study product or injection procedure, AEs resulting in discontinuation of study product, and serious AEs.

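### Does putting study completion on the both-cheeks FAS in SAP 6.1 hide treated subjects who leave early?

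*SAP*

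**What the plan says.** On completion, SAP 6.1 reads: "The number and percentage of subjects in the FAS population who complete the study will be summarized". The same sentence goes on to promise numbers and percentages of non-completers by reason, without naming a population for them.

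The two analysis sets differ in how much treatment they require. For the FAS, SAP 5.1 has: "Includes all subjects who were injected in both cheeks". For safety, SAP 5.3 has: "The Safety Population includes subjects who were injected in at least one cheek".

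Other parts of the plan cover treated subjects more widely:

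- SAP 6.1 also tabulates how many subjects were screened and treated, and the size of the FAS, Safety and PP sets.
- SAP 6.1 adds a listing: "All withdrawn subjects will be listed including subject number, date, reason for withdrawal, and last visit performed". Protocol 10.8 has the same requirement: "All withdrawn subjects will be listed individually".
- Exposure is on the wider set (SAP 7.3): "Data for injection characteristics will be summarized for initial treatment and optional touch-up for the safety population".
- The by-subject listings in SAP 7.4, on the Safety Population, include "AEs resulting in discontinuation of study product, and serious AEs".
- At site level, Protocol 5.5 requires: "All discontinuations and the reason for discontinuation are to be documented by the Investigator".

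**The concern.** A disposition table is normally expected to account for everyone who was treated. Here the completion rate starts from a set that already excludes anyone whose second cheek was not treated. If a subject stops after one side, for example because of an event during the first injection, and then leaves the study, she is in neither the numerator nor the denominator of the completion rate. If the FAS base carries over to the second half of the sentence, which is the natural reading but is not stated, she is missing from the reason percentages too.

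At stake is a completion rate that looks better than the experience of all treated subjects, on a different denominator from the exposure and adverse event tables. In an open-label study of about 60 subjects, even one or two such cases would show in the percentage.

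**Working it through.** The plan states no completion or dropout rate, and SAP 4.1 says the sample size does not come from a calculation, so there is no planned figure to reproduce. The check is set logic plus an illustration.

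**Set logic.** Everyone in the FAS is also in the Safety Population. The difference between the two sets is exactly the subjects treated on one side only. Any such subject who leaves is counted in Safety but not in FAS completion.

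**Inputs.**

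- N = 60 treated (planned size, SAP 3.2 and 4.1).
- k = one-cheek subjects who leave: not given, assumed 0 to 3.
- w = withdrawals within the FAS: not given, assumed 0 or 3.
- No one-cheek subject stays to the end (assumption, for simplicity).

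**Formulas.** Discontinuation on the FAS = w / (60 − k). Discontinuation among all treated = (w + k) / 60.

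| k | w | FAS | All treated |
|---|---|---|---|
| 0 | 0 | 0/60 = 0% | 0/60 = 0% |
| 1 | 0 | 0/59 = 0% | 1/60 = 1.7% |
| 2 | 0 | 0/58 = 0% | 2/60 = 3.3% |
| 3 | 0 | 0/57 = 0% | 3/60 = 5.0% |
| 0 | 3 | 3/60 = 5.0% | 3/60 = 5.0% |
| 1 | 3 | 3/59 = 5.1% | 4/60 = 6.7% |
| 2 | 3 | 3/58 = 5.2% | 5/60 = 8.3% |
| 3 | 3 | 3/57 = 5.3% | 6/60 = 10.0% |

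Each one-cheek leaver adds 1/60 = 1.7 percentage points to the all-treated rate.

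**What a reader can recover from the planned outputs.** Take k = 3 and w = 3. The disposition table would show 60 in the Safety Population, 57 in the FAS and 57 − 3 = 54 FAS completers. Safety minus FAS is 60 − 57 = 3, so the three one-sided subjects are visible at once. Before opening any listing, completion among all treated must lie between 54/60 = 90.0% (none of the three completed) and (54 + 3)/60 = 95.0% (all three did). The withdrawal listing, which is not limited to the FAS, settles which, and gives the reasons. Only those three subjects need looking up.

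**The case for a change.** The strongest argument for changing the denominator is one of purpose. SAP 5.1 presents the FAS as the set for effectiveness, and disposition is not an effectiveness analysis. Exposure and adverse events are on the Safety Population, so attrition cannot be read beside them on one base. The SAP itself provides for one-sided treatment by defining two sets, so the case is foreseeable. The population counts show how many treated subjects were left out of the rate, but not whether they finished or why they left. SAP 6.1 also asks for disposition by treatment group. The group sizes are not visible, but if they were 30 each (assumption), one such subject would shift a group's all-treated rate by 1/30 = 3.3 points. The change would cost a few words and one table row, with no new data.

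Most of this stands as a preference about table layout. All-treated disposition is arguably the better convention, and naming the denominator for the reason percentages would be tidier. It does not show an error, for three reasons.

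- The FAS base has its own logic. Effectiveness and demographics use the FAS, and SAP 4.5 relies on observed cases without imputation, so completion within the FAS tells the reader how complete the effectiveness data are.
- The rate is labelled as an FAS rate and stands beside the Safety and FAS counts, so it does not mislead.
- The missing detail is in a listing that the plan already requires, for a handful of subjects at most.

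**Conclusion.** The observation is right and no change to the plan follows. Completion is on the FAS by the SAP's own words; for the discontinuation reasons the FAS is only the likely reading. The effect depends on there being subjects treated in one cheek only who then leave. The documents neither predict nor exclude such subjects, and the visible text of the treatment procedure and of Protocol 10.2 is too limited to say more. Under the assumptions shown, one to three leavers among 60 treated would open a gap of 1.7 to 5.0 percentage points with no other withdrawals. With three FAS withdrawals as well, the gap would be 6.7% − 5.1% = 1.6 to 10.0% − 5.3% = 4.7 points. With none, the gap is zero.

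Whatever the number, the subjects remain in the treated and Safety counts, in the withdrawal listing, and in the exposure and adverse event outputs. No effectiveness or safety conclusion would differ. An analyst who meets such a case can footnote the table or add an all-treated row without amending anything.

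Two nearby slips are clerical and affect no discontinuation figure. SAP 6.1 counts subjects as randomized, although Protocol 4.4.1 says randomization does not apply. SAP 6.4 refers to an ITT population that SAP 5 does not define; the FAS used for demographics in SAP 6.3 is the obvious reading.

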6.2 Protocol Deviations

Protocol deviations will be presented by subject in a data listing. Subjects with protocol deviations will be listed individually, including subject number and observed deviation.

Sponsor: Galderma

Protocol Number: CTN 05DF2004

Doc id
[REDACTED]

Plan Version: 1.0

Subjects may be excluded from the PP population based on the seriousness of the deviation, which shall be documented prior to database lock.

6.3 Demographics and Baseline Characteristics

Demographic endpoints, baseline assessments, and subject characteristics will be presented based on the FAS set using descriptive statistics by treatment, as appropriate. The variables to be summarized are described below:

- Continuous variables
 - Age (years)
 - Weight (kg)
 - Height (cm)
 - Body Mass Index (BMI) (kg/m²)
- Categorical variables
 - Race (White, Black or African American, Asian, American Indian or Alaska Native, Native Hawaiian or Other Pacific Islander, Other)
 - Ethnicity (Hispanic or Latino, Not Hispanic or Latino)
 - Fitzpatrick Skin Types (FST) (I, II, III, IV, V, VI)

If variables are collected at screening and baseline, the baseline value will be summarized. Demographic and baseline characteristics will be presented by treatment and subject in a data listing.

6.4 Medical History

History of relevant surgical events and medical conditions, including any prior dermatological procedures or implants, are collected.

Medical history will be summarized by individual treatment group and overall for the ITT population as given below:

- i) Any Medical History
- ii) Prior Dermatological Procedures or Implants

Each summary will separate events by system organ class (SOC) and preferred term (PT). Each subject will only be counted once per SOC and PT.

Medical history and Prior Dermatological Procedures/Implants history will be reported by treatment and subject in separate data listings.

Title
05DF2004 SAP

Advanced Clinical

Doc id

Sponsor: Galderma

Protocol Number: CTN 05DF2004

Plan Version: 1.0

7.0 EFFICACY ANALYSIS

7.1 Primary Efficacy

7.1.1 Primary Efficacy Endpoint

The primary efficacy endpoint is [REDACTED]
assessed by the Treating Investigator week 4 after last treatment compared to
pre-treatment.

Effective

Version: 1.0

Very much worse

Obvious worsening in appearance from the initial condition.

7.1.2 Primary Efficacy Analysis

7.2 Secondary Efficacy

7.2.1 Secondary Efficacy Endpoints

7.2.2 Secondary Efficacy Analysis

All secondary analysis will be done using the FAS population.

Title

Advanced Clinical

Doc id

Sponsor: Galderma

Protocol Number: CTN 05DF2004

Plan Version: 1.0

Effective

Version: 1.0

Topic	Percentage
Healthcare	98
Technology	95
Finance	92
Politics	90
Entertainment	88
Science	85
Food	82
Sports	78
Business	75
Art	72
History	68
Geography	65
Mathematics	62
Chemistry	58
Physics	55
Biology	52
Physics	50
Chemistry	48
Biology	45
Mathematics	42
Geography	40
History	38
Art	35
Business	32
Sports	30
Food	28
Science	25
Entertainment	22
Technology	20
Politics	18
Finance	15
Healthcare	12
Other	10

SAFETY ANALYSIS

7.3 Drug Exposure and Compliance

Data for injection characteristics will be summarized for initial treatment and optional touch-up for the safety population. The following parameters will be summarized for extent of exposure:

- Injection Volume and Total Injection Volume (initial plus touch up)
- Injection Depth
- Injection Method
- Needle Size

The extent of exposure data will also be presented by subject in a data listing.

7.4 Adverse Events

Adverse events (AEs) will be summarized for the safety population. All AEs will be coded using MedDRA and presented by MedDRA system organ class (SOC), preferred term (PT), and treatment.

Only AEs occurring after first injection will be included in analysis. AEs occurring before, if any, will only be listed in subject data listings.

All AE endpoints will be summarized by treatment group - Restylane® Volyme and Restylane® Lyft.

A summary of AEs will be provided, which will include:

- i) number of subjects with at least one AE and number of events (in total as well as serious AEs)
- ii) number of subjects with at least one AE, related to study product or injection procedure, and number of events (in total as well as serious AEs)
- iii) number of subjects with at least one AE, unrelated to both study product and injection procedure, and number of events (in total as well as serious AEs)
- iv) number of subjects who did not have an AE

AEs will be summarized by SOC, PT, and severity.

The number of subjects with AEs related to study product or injection procedure as well as the number of events will be summarized by SOC, PT, and severity.

In addition, for related AEs, the number of days to onset and the duration of event will be summarized by SOC and PT using mean, SD, min, max and median.

Time to onset of an AE will be derived as the start date minus the date of most recent treatment. If the start date is missing, it will be assumed that the AE started on the day of most recent treatment.

Duration of an AE will be derived as the stop date minus the start date + 1. If the start date is missing, it will be assumed that the AE started on the day of most recent treatment. Missing stop date will not be imputed and therefore no duration will be calculated in these cases. Instead, the number of AEs that were ongoing at the end of the study will be given.

If a subject has more than 1 AE of the same PT and there are different grades of severity, only the highest grade will be represented in the summary of severity. If the severity assessment is missing, the highest level of severity will be assumed.

Action taken for related AEs will also be summarized.

All reported AEs will be listed in data listings including time to onset, duration of AE and timing of the AE. Timing would be the variable indicating whether the AE occurred after no treatment, initial treatment, or optional retreatment.

By-subject listings also will be provided for all subjects (safety population) for the following: AEs related to study product or injection procedure, AEs resulting in discontinuation of study product, and serious AEs.

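### Minor: a missing AE start date is replaced by a treatment date and used in the related-AE onset and duration summaries, so onset is 0 by construction and duration can err either way

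*SAP*

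**What the plan says.** SAP 7.4 derives two quantities for each AE. Onset: "Time to onset of an AE will be derived as the start date minus the date of most recent treatment". Duration: "Duration of an AE will be derived as the stop date minus the start date + 1". After each formula it gives the same rule for an undated event: "If the start date is missing, it will be assumed that the AE started on the day of most recent treatment".

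A missing stop date is handled differently: "Missing stop date will not be imputed and therefore no duration will be calculated in these cases". The section continues: "Instead, the number of AEs that were ongoing at the end of the study will be given".

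The derived values are used as follows: "for related AEs, the number of days to onset and the duration of event will be summarized by SOC and PT", with mean, SD, minimum, maximum and median. They also appear in the AE listings, beside a further variable: "Timing would be the variable indicating whether the AE occurred after no treatment, initial treatment, or optional retreatment". On inclusion, the SAP says: "Only AEs occurring after first injection will be included in analysis".

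Section 7.4 gives no reference point for the most recent treatment, and no rule flags or excludes assumed starts. SAP 4.5 and Protocol 10.6 both state an observed-case approach without imputation and name no exception for AE dates. SAP 7.4 also assigns the highest severity when severity is missing, which is another unlisted exception.

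**The concern.** A subject can be treated twice, so a rule that points to the latest treatment does not always point to the treatment the event followed. The assumed date is not kept apart from observed dates. It enters the same mean, SD and range, and in a preferred term with few events it can set the minimum. Onset suffers most, because the assumed start and the reference date are the same day, so the resulting 0 carries no information about the event. Within the same paragraph a missing stop date leads to no calculation, while a missing start date leads to a calculated value.

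What is at stake is the descriptive picture of when related reactions begin and how long they last, and the listing entry that assigns an event to the initial treatment or the touch-up.

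**Working it through.** The plan states no figure on this point, so there is none to reproduce. The check applies the SAP's own formulas.

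**Inputs**
- First injection: Day 1 (SAP 4.2).
- Touch-up: Protocol 8.1 places it at two weeks, so 1 + 14 = Day 15. This is an assumed nominal day, as the visit window is not visible.
- End of AE reporting: 8 weeks after last treatment (Protocol 8.2.4).
- Onset = start - treatment date. Duration = stop - start + 1 (SAP 7.4).

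**Step 1, onset.** With assumed start = treatment date, onset = treatment date - treatment date = 0, whichever treatment is meant. The true onset could be as late as 8 x 7 = 56 days. If a share f of related AEs lacks a start date and these events are otherwise typical, the summarised mean is (1 - f) x true mean. For an assumed true mean of 3 days and f of 5%, 10% or 20%, that is 2.85, 2.70 or 2.40 days.

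**Step 2, duration.** Take the assumed start as the latest treatment on or before the stop date. The error is true start - assumed start.

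| True event | Touch-up Day 15? | True duration | Assumed start | SAP duration | Error |
|---|---|---|---|---|---|
| Day 1-20 | yes | 20 | 15 | 20 - 15 + 1 = 6 | -14 |
| Day 2-20 | yes | 19 | 15 | 6 | -13 |
| Day 8-20 | yes | 13 | 15 | 6 | -7 |
| Day 14-20 | yes | 7 | 15 | 6 | -1 |
| Day 2-8 | yes or no | 7 | 1 | 8 - 1 + 1 = 8 | +1 |
| Day 8-14 | yes or no | 7 | 1 | 14 - 1 + 1 = 14 | +7 |

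An event that spans the touch-up loses 1 to 14 days. An event that ends before it, or in a subject without one, gains exactly its true onset.

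**Step 3, the last-treatment reading.** If the rule is coded as the last treatment the subject received, the assumed start is Day 15 whatever the stop date. Stop Day 8 gives 8 - 15 + 1 = -6. Stop Day 14 gives 14 - 15 + 1 = 0.

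**Step 4, what a stop-date condition would do.** Requiring the assumed start to be on or before the stop date changes the Step 3 results to 8 and 14. Step 2 already includes that condition, so the spanning events still get 6 days, and Step 1 still gives 0.

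**Step 5, effect on a summary.** One event shortened by 13 days lowers the mean of a preferred term with 5, 10 or 20 durations (assumed sizes) by 13/5 = 2.6, 13/10 = 1.3 or 13/20 = 0.65 days.

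**The case against.** The strongest defence is that the assumption is prespecified and often close. Injection-related reactions of the kind listed in Protocol 8.2.9 tend to begin at once, so onset 0 and a start on the treatment day are near the truth, and a related event has a natural anchor that an ongoing event lacks. Start date is recorded for every AE (Protocol 8.2.3) and data are queried (Protocol 9.2.2). Excluding events discards some information. All of this stands, and it is why the point is minor. It does not help a later event, or one carried across the touch-up.

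The shortening also depends on the reading. AEs are asked about at every visit and the touch-up is Visit 3. If the rule means the latest treatment before the event was first reported, a Day 2-20 event reported before that injection keeps a Day 1 start and gets 20 days, one too many. The order of procedures at Visit 3 is not visible, so this reading cannot be excluded. It confirms that the wording is open, and onset is still 0.

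Four stronger readings are tempting, but the documents do not support them:
- That the missing link to the stop date causes the shortening. Step 4 shows it does not. The link would prevent only zero or negative durations.
- That the SAP will produce negative durations. They arise only under the last-treatment reading, which fits poorly with the onset formula and the Timing variable.
- That the SAP already counts missing stop dates. It counts AEs ongoing at study end, which is not the same thing. The precedent is only that no duration is calculated.
- That 7.4 breaches the no-imputation rule in substance. A specific rule can override a general one, so this part is a matter of cross-reference.

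**Conclusion.** The point holds as a minor one. Under SAP 7.4 every related AE with a missing start date is summarised with onset 0. Its duration may be up to 14 days too short if it spans a Day 15 touch-up, or too long by its true onset otherwise. The net direction across events is unknown. The wording also leaves room for a programming choice that yields impossible durations.

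The sizes rest on the assumed Day 15 touch-up and on illustrative events. The documents give no expected number of missing start dates, and the shares and preferred-term sizes used above are assumptions. The effect is confined to the related-AE onset and duration summaries and to the listings. Nothing here supports a doubt about AE counts, the primary endpoint or the overall safety analysis.

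**What to change.** In SAP 7.4:
- Do not calculate onset or duration when the AE start date is missing, and report the number of such AEs next to the two summaries. This agrees with SAP 4.5 and Protocol 10.6, and with the existing choice not to calculate a duration when the stop date is missing.
- Keep these AEs in the AE counts as occurring after first injection, consistent with Protocol 8.2.4, unless the stop date shows otherwise.
- In the listing, show Timing as unknown when the subject had a touch-up and the stop date is on or after it or is missing. Assigning such an event to the latest treatment before its stop date would repeat the misattribution.

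In SAP 4.5, add a cross-reference naming any AE rules kept in 7.4, such as worst-case severity, as exceptions.

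The cost is a short paragraph in 7.4, a sentence in 4.5 and a small programming change using AE and treatment dates already collected. The downside is that a few events drop out of two descriptive summaries, including some immediate reactions for which the assumed date would have been about right.
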